7.2.6 Criteria for Subject Withdrawal

Subjects can decide to withdraw from the investigation at any time. The Investigator shall ask the reason(s). The reason for withdrawal should to be documented in the subject's source files and the case report form (CRF).

The Investigator or Sponsor may also decide to withdraw a subject from the clinical investigation if it is considered to be in their best interest.

Subject withdrawal may be for any of the following reasons:

- Adverse Event (AE)
- Device Deficiency (DD)
- CIP or GCP deviation
- Subject lost to follow-up
- Subject withdrew consent
- Subject death
- Sponsor decision
- Investigator decision

If subject withdrawal is due to problems related to the investigational device, safety or performance, the Investigator shall ask for the subject's permission to continue in safety follow up (i.e., adverse events) until their scheduled End-of-Investigation visit.

If a subject is lost to follow-up, every possible effort must be made by the investigation site personnel to contact the subject and determine the reason for discontinuation. At least 3 separate attempts taken to contact the subject must be documented.

Enrolled subjects who are withdrawn/discontinued will not be replaced.

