9 STATISTICAL CONSIDERATIONS

9.1 General Considerations

The distribution of continuous variables as well as change in continuous variables will be given as n, mean, SD, SEM, Median, Min and Max and the distribution of dichotomous and categorical variables will be given as number and percentages. Mean changes over time will be presented along with 95% CI.

All data will be presented in summarized tables and figures along with listings of individual data. The last non-missing measurement from the CBAS5751 investigation (3- and 6-months visits) will serve as the baseline reference in this follow up analysis for each subject. Changes from this baseline measurement will be evaluated statistically using a paired statistical methodology, each subject serves as his/her own control. Data collected at 12 and 24 months will be presented by visit where applicable. Data which are of collected continuously over time such as Adverse event and Device deficiency will be presented as Number of events and Number of subjects with events, and not by visits. Efficacy audiology measurements will be compared to the subjectively evaluation of the satisfaction with the system in order to find out if there are any useful clinical audiological cut-offs where a subject is satisfied or not.

Analyses at 12 months will be based on subjects attending the 12 months visit and analyses at 24 months analyses will be based on subjects attending the 24 months visit. No per protocol analyses will be performed and no imputation of missing data will be made.

Pass/fail criteria to be applied to the results:

- The objective is considered as fail if more than two of the subjects have experienced a related serious adverse event with the same root cause within the first 24 months from surgery.
- The objective is considered as fail if more than two of the subjects have an increase in PTA-4 Sound field threshold >15 dB at 24 months compared to the last obtained aided PTA value in CBAS5751 (3 or 6 months).
- The objective is considered as fail if more than two of the subjects have an increase in SNR field threshold >1 unit at 24 months compared to the last obtained aided SNR value in CBAS5751 (3 or 6 months).

If a failed result regarding PTA-4 or SNR is obtained a root cause analysis will be performed to confirm that the failed value depends on declined performance and not on other factors such as impaired unaided hearing, incorrectly performed tests or other causes.

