11.2 Recording and Handling of Adverse Events

Subjects shall be carefully monitored during the clinical investigation and the investigator should enquire about AEs at each visit.

All AEs will be recorded from the last visit in the CBAS5751 investigation. AE recording will continue for each subject until completion of the final visit. Ongoing SAEs, SADEs and/or AESI will be followed for 30 days, or until resolution or stabilisation of the event, whichever comes first.

Source notes should indicate the evaluation for AEs, even if none to report. All required AEs will be reported if observed, even if anticipated and/or acknowledged as a risk factor in the consent.

All AEs will have the following information documented: start and stop dates, action taken, outcome, severity and investigators opinion on the potential relationship to the Investigational device and investigational procedures. If an AE changes in severity, the most severe (highest) grade will be captured for that event on the Adverse Events CRF.

Adverse events will be summarized by either IMDRF or CTCAE to System Organ Class (SOC) and IMDRF/CTCAE term. Decision will be taken in due time before database lock.

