17 SUSPENSION OR PREMATURE TERMINATION

The Sponsor will discontinue the clinical investigation site if:

- 1) major non-adherence to the CIP or GCP principles is occurring
- 2) it is anticipated that the subject recruitment will not be adequate to meet the objectives of the clinical investigation

An ongoing clinical investigation may be discontinued in case of:

- 1) device failure
- 2) serious or intolerable ADE, leading to the explant or discontinued use of the device
- 3) subject's death

Should the Sponsor discontinue the clinical investigation, the Sponsor will continue to support those subjects who were already implanted with the device under investigation until the IMD is approved by national regulatory authority.

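### Post-withdrawal follow-up is requested only for device, safety or performance withdrawals and only for adverse events, so later related SAEs in other withdrawn subjects go unseen and can only favour a pass

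*Combined protocol and SAP*

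**What the plan says.** Section 7.2.6 lists eight reasons for withdrawal: adverse event, device deficiency, CIP or GCP deviation, loss to follow-up, withdrawn consent, death, sponsor decision and investigator decision. It then gives one rule for data after withdrawal: "If subject withdrawal is due to problems related to the investigational device, safety or performance, the Investigator shall ask for the subject's permission to continue". The permission sought is for remaining "in safety follow up (i.e., adverse events) until their scheduled End-of-Investigation visit". For loss to follow-up it adds: "At least 3 separate attempts taken to contact the subject must be documented". Those attempts serve to establish why the subject left. On replacement: "Enrolled subjects who are withdrawn/discontinued will not be replaced".

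The first pass/fail criterion in section 9.1 fails the objective when "more than two of the subjects have experienced a related serious adverse event with the same root cause within the first 24 months from surgery". It is a number of subjects, not a proportion, and section 9.1 rules out imputation. One failed criterion fails the whole investigation.

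Section 11.2 sets the general recording period: "AE recording will continue for each subject until completion of the final visit". Device deficiencies are listed as a safety endpoint in section 9.2.1.

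**The concern.** Leaving this study does not end exposure. Subjects were implanted in CBAS5751, and section 7.2.8 lets them keep the device afterwards. Section 8.3 says the long-term risk is unknown and that this study will follow it to 24 months.

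Whether a later related SAE, explantation or revision is seen therefore depends on the reason recorded for leaving. A subject withdrawn for a protocol deviation has not refused contact, yet nobody is required to ask about events after that date. The same holds for a subject who leaves for convenience and would have accepted a telephone call.

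The loss works in one direction. With a fixed limit and no denominator, an event that is not seen can bring the count closer to a pass and never to a fail. A reader of the result would not know how many of the subjects behind the count were observed to month 24.

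**Working it through.** The plan gives no sample size, event rate or withdrawal rate, so there is no figure to reproduce. Withdrawal numbers and event risks below are assumptions.

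**1. Which withdrawals are affected**

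- *Adverse event, device deficiency:* on a natural reading, within the safety or performance trigger.
- *Death:* no later time to follow.
- *Loss to follow-up:* has its own contact rule.
- *Withdrawn consent:* permission is sought only if the reason is device, safety or performance. Others may be willing but are not asked.
- *CIP/GCP deviation, sponsor decision, investigator decision:* not covered when the reason is not a safety or performance one.

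The gap is the last group plus part of the consent group.

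**2. What stays in the count**

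Section 9.1 presents adverse events and device deficiencies cumulatively rather than by visit. Section 9.5 analyses anyone who attends the 12- or the 24-month visit. The Schedule of Events has visit 1 collect events back to the 6-month CBAS5751 visit. Events recorded before withdrawal therefore remain for a subject who attended visit 1. Only events after withdrawal are missing.

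**3. Observation time lost**

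Inputs: maximum 27 subjects (section 7.2.3) and a window of 24 months from surgery (section 9.1).

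Planned time = 27 × 24 = 648 subject-months. If k subjects leave at month 12, the loss is k × (24 − 12).

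- k = 1: 12 / 648 = 1.9%
- k = 3: 36 / 648 = 5.6%
- k = 5: 60 / 648 = 9.3%

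If they leave at month 18, the loss halves: 6, 18 or 30 of 648 (0.9%, 2.8%, 4.6%).

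**4. Effect on the verdict**

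Let p be the true 24-month risk per subject of a related SAE of one given root cause, with subjects independent. With complete follow-up,

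P(fail) = 1 − Σ C(27, x) pˣ (1 − p)²⁷⁻ˣ, summed over x = 0, 1, 2.

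At p = 0.10: 1 − (0.05815 + 0.17445 + 0.25198) = 0.515.

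If w subjects leave at month 12 and half of their risk falls before then, the observed count is Bin(27 − w, p) + Bin(w, p/2):

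| p | complete | w = 2 | w = 3 | w = 5 |
|---|---|---|---|---|
| 5% | 0.150 | 0.139 | 0.133 | 0.122 |
| 10% | 0.515 | 0.489 | 0.476 | 0.449 |
| 15% | 0.793 | 0.770 | 0.758 | 0.732 |

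The probability of a fail drops by about 1 point (5%, w = 2: 0.150 − 0.139) to 7 points (10%, w = 5: 0.515 − 0.449), always towards a pass.

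**5. When one event decides**

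A fail needs three subjects with the same root cause. One unseen subject changes the verdict only when the observed count for that cause is exactly two. Section 4.2.2.1.2 reports two related SAEs in CBAS5751, both post-operative wound infections. Whether they came from two subjects who enrol here, and would be judged to share a root cause, is not settled in the documents.

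**The case against.** The best defence is that the gap is narrow. The trigger names safety and performance as well as the device, so it can be read to cover most withdrawals that matter for safety. Some sponsor or investigator withdrawals made in the subject's interest would also qualify. Refused consent cannot be overridden. The study is descriptive, without formal hypothesis testing. All of this stands and limits the size of the point. It does not supply a request for follow-up where none is written.

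Several stronger readings are tempting, and the documents do not support them.

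- *Withdrawn subjects vanish from the safety count.* Sections 9.1 and 9.5 keep their earlier events. Section 9.1 also bases the 24-month analyses on 24-month attenders, and it does not say whether that reaches criterion 1. This calls for a clarifying sentence but does not show that the events are removed.
- *Section 7.2.6 contradicts sections 9.1 and 11.2.* Those sections set a general recording period and a criterion window; 7.2.6 is the specific rule for withdrawn subjects. The fair statement is that the general period is not provided for in some withdrawn subjects.
- *The loss is 4%, 11% or 19%.* That divides by 27 × 12 = 324 subject-months, the time between the two visits. Criterion 1 runs for 24 months from surgery, so 648 is the matching denominator.
- *Omitting device deficiencies could change the verdict.* They enter none of the three pass/fail criteria. Their omission weakens a safety endpoint only.
- *Site closure for poor recruitment under section 17 is part of this problem.* It is a separate matter, and subject loss by that route is speculative.

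**Conclusion.** The point holds as a limited, one-directional gap. Section 7.2.6 makes follow-up depend on the reason for withdrawal and restricts it to adverse events. Some subjects who still carry the implant, and have not refused contact, then have no planned safety collection after they leave. Criterion 1 has no denominator that would reveal this.

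The size is modest: 1.9% to 9.3% of subject-months for one to five withdrawals at month 12, and about 1 to 7 percentage points on the probability of a fail in the scenarios shown for two to five withdrawals. These figures rest on assumed withdrawal numbers, assumed event risks and half of the risk falling after month 12. The two related SAEs in CBAS5751 were perioperative. If risk is concentrated early, less is lost after month 12 and the effect is smaller. Those two events are not evidence about the rate in the second year.

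**What to change.** In section 7.2.6, replace the conditional request with one that applies to all, for example: *For every withdrawn subject, whatever the reason, the investigator asks permission to go on collecting adverse events (including explantation and revision surgery) and device deficiencies, by telephone or from records, up to 24 months after surgery.* Put matching wording in the consent form.

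In section 9.1, state that related SAEs recorded before withdrawal count towards criterion 1. Report beside that criterion how many subjects have complete safety ascertainment to 24 months.

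The cost is a few sentences, consent wording and a small number of extra contacts. Some subjects will decline, and remote reports will be less detailed than a visit. Refusal remains the subject's right, and the ascertainment figure makes its extent visible.

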7.2.7 Randomisation Procedures

Not applicable

7.2.7.1 Blinding Procedures

Not applicable

7.2.8 Post-investigation Medical Care

After the clinical investigation the subjects will be able to continue with their Investigational device. Routine controls with audiological checks will follow local routines according to the standard treatment program for bone conduction hearing implant systems. The Investigational device will be warranted and supported with service according to normal regional Cochlear routines.

7.3 Performance Evaluations and Procedures

7.3.1 Demographics

The following demographic data will be collected from the previous CBAS5751 investigation:

- Age collected as date of birth (month and year)
- Gender
- Race
- Nicotine use (Cigarettes/day)

7.3.2 Post-Enrolment Evaluations and Procedures

7.3.2.1 Audiometry testing

If the study team experience an "unreasonable value" in any test, the test should be performed again after a short while to confirm validity.

7.3.2.1.1 Audiogram

To follow how the subject's hearing thresholds change over time, unaided audiometric threshold measures (including both air- and bone conduction thresholds) will be recorded at 12 and 24 months and compared with the same data collected at baseline before implantation in the CBAS5751 investigation.

Frequencies required for air conduction thresholds are 250, 500, 750, 1000, 1500, 2000, 3000, 4000, 6000 and 8000Hz. For bone conduction thresholds the required frequencies are 250, 500, 750, 1000, 1500, 2000, 3000, 4000 and 6000Hz.

7.3.2.1.2 General instructions for audiological assessments

A detailed work instruction regarding the audiological assessments will be available during training before the start of the investigation.

All tests shall be performed in a sound insulated room. Equipment used for audiological testing shall be calibrated according to the clinic's normal standard before initiation of the investigation. The speakers should be at the height of the test subject's head and more than 1 meter away from the test subject. There should preferably be more than 1 meter of free space around the test subject in all directions. This is in accordance with the current standard (14). It is important to keep the same sound room and test equipment set-up during the entire clinical investigation. ***Changes may be necessary and allowed, but only after approval by the Sponsor.***

7.3.2.1.2.1 Blocking

All audiometric tests shall be performed with the non-test ear blocked (in case of normal or near-normal hearing or a large asymmetry with the non-test ear having significantly better hearing thresholds). Before blocking of the non-test ear, a sound-field measurement on PTA4 frequencies (500, 1000, 2000, 4000 Hz) shall be performed. The blocking shall then be done with earplug and muff and an additional sound-field measurement on PTA4 frequencies shall then be performed to verify effective blockage and document the hearing level after blockage.

7.3.2.1.2.2 Settings for the Sound Processors

The Investigational device should be tested using the Everyday program, with active gain disabled.

7.3.2.1.3 Audiological assessments

7.3.2.1.3.1 Sound Processor fitting

OFS (version 2) will be used to adjust the Investigational device settings for a specific subject. This will be performed during fitting at the 12- and 24-month visit and at an extra visit if needed (for example if the magnet is replaced with a different strength or start/stop of use of a soft pad). If the gain needs to be adjusted or changes to the program configuration are needed, a fine tuning is recommended. The fitting software will be installed on a laptop computer provided by the Sponsor, and the fitting-data will be saved on the laptop until the investigation is ended when it will be transferred to the Sponsor in a coded way.

Coil-to-coil measurement

The Digital Link Calibration (e.g. coil-to-coil measurement) that is a step in the connection step in the OFS, should be performed at each occasion the software is being used to fit or finetune the device to optimise the performance of the device for the user throughout the investigation. This will also provide an indication of the soft tissue thickness during the course of the investigation.

7.3.2.1.3.2 Bone Conduction (BC) Direct

BC Direct is a tool in the OFS (current version) to establish the unmasked bone conduction threshold with tones presented through the sound processor. BC Direct measurements (as part of the OFS) will be performed at 12 and 24 months when the subject is using the Investigational device. BC thresholds obtained at the following frequencies will be recorded; 250, 500, 750, 1000, 1500, 2000, 3000, 4000, 6000 Hz.

7.3.2.1.3.3 Sound-field thresholds

The purpose of this test is to establish the hearing thresholds in free field through a speaker in front position (0 degrees azimuth) according to the so-called ascending or modified Hughson-Westlake method (Figure 3). The frequencies to be tested are [0.25, 0.5, 0.75, 1.0, 1.5, 2.0, 3.0, 4.0, 6.0 and 8.0 kHz], the signal to be used shall be warble tones.

[figure not shown]

Figure 3: The setup of the speaker when testing sound-field thresholds.

7.3.2.1.3.4 Speech test

Adaptive Speech recognition in noise

The purpose of this test is to establish the test subject's ability to recognize speech in the presence of background noise. The adaptive speech test in noise shall be conducted using validated lists for the language it is presented in. The first list shall be used as a training list before the test is performed and the training list shall be used at each visit. Both speech and noise will be presented in sound field from the front speaker (0 degrees azimuth, S_0N_0) (Figure 4). In Hong Kong software and speech material to be used is the CHINT (8), where the noise shall be kept constant at 65 dB SPL, and the speech shall be adapted stepwise according to the software used to establish the signal-to-noise ratio (SNR) where the test subject repeats 50% of the material correctly. In Melbourne and Sydney, the test to be used is AuSTIN (9), where the sentences shall be presented at a constant level of 65 dB SPL throughout the test, and the babble noise shall be adapted stepwise according to the software used to establish the speech-to-noise ratio (SNR) providing a 50% level of correctly repeated morphemes.

[figure not shown]

Figure 4. The setup of the speakers when testing Adaptive Speech recognition in noise.

This measurement shall be performed with the Investigational device at 12 and 24 months.

7.3.2.1.3.5 Cochlear Device Image (CDI) tool

The CDI tool is an engineering software used to establish the unmasked bone conduction high frequency thresholds with tones presented through the sound processor. The CDI measurements will be performed at 12 and 24 months when the subject is using the Investigational device. The CDI thresholds obtained at the following frequencies will be recorded; 6, 7, 8, 9 and 9.5 kHz.

7.3.2.2 Patient reported outcomes

7.3.2.2.1 Abbreviated Profile of Hearing Aid Benefit (APHAB form A)

The APHAB form “A” questionnaire (10) from HARL (Hearing Aid Research Lab, University of Memphis, USA) is a 24-item self-assessment inventory that evaluates the benefit experienced by the subject when using hearing amplification compared to the unaided listening. APHAB produces a global score and scores for four subscales: Ease of Communication, Reverberation, Background Noise, and Aversiveness.

The subjects will complete the APHAB questionnaire at 12 and 24 months follow up for the aided situation (with the Investigational device).

The APHAB questionnaire is available for free and in different languages on the HARL home page.

7.3.2.2.2 Speech, Spatial and Qualities of Hearing Scale (SSQ-12 version)

The short form of Speech, Spatial, and Qualities of Hearing Scale questionnaire (SSQ-12) (15) from MRC Institute of Hearing Research, UK, is a scaled-down version of the 49 items SSQ questionnaire (11). It is designed to compile a sub-set of items from the longer original 49 version to represent the scale as a whole, measuring self-reported auditory disability, reflecting the reality of hearing in the everyday world. It has been shown to provide similar results to SSQ49 (15). It covers:

- Hearing speech in a variety of competing contexts
- The directional, distance and movement components of spatial hearing
- Segregation of sounds and attending to simultaneous speech streams
- Ease of listening
- The naturalness, clarity and identifiability of different speakers, different musical pieces and instruments, and different everyday sounds

The subjects will complete the SSQ questionnaire at the 12- and 24-months follow-up for the aided situation (with the Investigational device).

The SSQ-12 questionnaire is free for use, confirmed by [REDACTED], former Director of MRC Institute of Hearing Research, which closed down 2018.

7.3.2.2.3 Health Utilities Index (HUI)

HUI® (12) is a generic preference-based system for measuring comprehensive health status and health-related quality of life (HRQoL). HUI provides descriptive evidence on multiple dimensions of health status, a score for each dimension of health and an overall health-related quality of life (HRQoL). The scoring systems provide utility (preference) scores on a generic scale where dead = 0.00 and perfect health = 1.00. HUI3 will be used in this clinical investigation (Questionnaire HUI23S1EN.15Q). The HUI3 classification system is comprised of 8 attributes: Vision, Hearing, Speech, Ambulation, Dexterity, Emotion, Cognition and Pain – each with 5 or 6 levels of ability/disability (12). The version in this clinical investigation uses a recall time of 1 week.

The subjects will complete the HUI at the 12- and 24-months follow-up for the aided situation (with the Investigational device).

The license to use the HUI questionnaire is purchased from Health Utilities Inc., [name].

